# 8.2 Summary of Product Characteristics (SmPC)

The Electronic Medicines Compendium has an SmPC for acetazolamide and furosemide solution for infusion which have been used to write the protocol.

# 8.3 Drug storage and supply

The trial drug and active comparator will be available from the pharmacy at CHH from normal hospital stock. All acetazolamide tablets for the entire study will be dispensed on the day of randomisation from the pharmacy upon receipt of a suitably signed trial specific electronic prescription. The medications will be stored in labelled boxes securely on the ward and made available to the patient at during the morning and afternoon drug rounds by the nursing staff on the ward. The study doctor visit will be around the time of the first dose to monitor adherence and address any concerns. Any tablets that are not taken for whatever reason will be returned to the hospital pharmacy for destruction. There will be no arrangements for post-trial access to acetazolamide. The active comparator will be prescribed by the patient's clinical team and given by nursing staff on the ward from ward stock.

# 8.4 Preparation and labelling of Investigational Medicinal Product (IMP)

Eight acetazolamide 250mg tablets will be dispensed into a suitable container and labelled according to Annexe 13.

# 8.5 Dosage schedules

The acetazolamide will be taken orally as it has good oral bioavailability (70-90%) reaching peak concentrations after 2 hours with a plasma half life of 4 hours. All other adjunctive diuretics are routinely given orally in the UK – e.g. Bendroflumethiazide, metolazone, dapagliflozin, empagliflozin.

ACZ will be given in the morning and again 6 hours later so that the maximal diuretic effect occurs in the daytime to reduce the chance of the patient waking in the night. The maximum daily dose is 500mg in maximum split doses of 250mg. There will be no individualised dosing. Duration of treatment is 4 days. Furosemide infusions will be continuous as long as is clinically indicated and replenished as and when required.

# 8.6 Dosage modifications

There are no planned dose modifications.

# 8.7 Known drug reactions and interaction with other therapies

Acetazolamide is currently licenced to treat glaucoma and epilepsy, and is used in the prophylaxis of high altitude pulmonary oedema.

#### **Common or Very** Uncommon **Rare or Very Rare Unknown frequency** Common Haemorrhage Bone marrow disorders Anaphylaxis Agranulocytosis Metabolic acidosis Depression Loss of appetite Drowsiness Confusion / Irritability Paraesthesia Dizziness Myopia Nephrolithiasis Electrolyte disturbance Fatique Polvuria Hepatic disorders Diarrhoea Suicidal behaviour Hearing impairment / Fever / Flushing Altered taste tinnitus Leucopoenia Headache Thirst Decreased libido Nausea / Vomiting Agitation Symptoms of nephrolithiasis Paralysis Rash Seizure Thrombocytopenia Ataxia Osteomalacia Hyperglycaemia Hypoglycaemia Renal tubular necrosis

# Side Effects of Acetazolamide Taken from The British National Formulary

The early studies suggested that side effects such as drowsiness and paraesthesia are seen in 14-38% of patients with heart failure at doses >1000mg per day, although side-effects were less common at doses  $\leq$ 500mg per day (5-10%). Modern day studies did not report any adverse events but it is not explicitly stated that this is due to the medication being well tolerated.

Common or Very Common	Uncommon	Rare or Very Rare	Unknown frequency
Dizziness;	Diarrhoea	Bone marrow depression	Deafness
Electrolyte imbalance		Photosensitivity reaction	Leucopoenia
Fatigue			Paraesthesia
Headache;			Rash
metabolic alkalosis;			Thrombocytopenia
Muscle spasm			Tinnitus
Nausea			Vomiting

# Side Effects of Furosemide Taken from The British National Formulary

# 8.8 Concomitant medication

Due to possible drug interactions with acetazolamide patients taking high dose aspirin (>500mg / day), methotrexate, lithium, or sodium valproate will be ineligible for the study unless these medications have been discontinued >48 hours previously patients concurrently taking these medications will be excluded. Patients taking other drugs that have a notable diuretic effect thiazide and thiazide-like diuretics, and sodium-glucose co-transporter 2 inhibitors (SGLT2I) will be excluded.

Loop diuretics are commonly given to patients with heart failure, as a general rule there are no concomitant medications that would restrict the use of intravenous furosemide in patients who have severe oedema.

# 8.9 Trial restrictions

There are no dietary requirements or restrictions however patients will be required to complete diet sheets detailing all oral intake during the study. Starting sodium-glucose co-transporter 2 inhibitors or thiazide and thiazide-like diuretics will be contraindicated during the 4 days of treatment with ACZ unless the patient is deemed euvolaemic and ready for discharge in which case it may be clinically appropriate to start an SGLT2I for morbidity and mortality benefit if the patient has left ventricular systolic dysfunction – this decision would be taken by the treating team and not the study team.

Patients with COVID-19 infection which is **not** thought to be contributing to their symptoms – incidental diagnosis – are still eligible for the trial. Similarly, if a patient becomes COVID-19 positive during the study they can continue.

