# 4 TRIAL DESIGN

This will be an open label, randomised, controlled pilot and exploratory study which will be powered to detect superiority of the addition of acetazolamide 250mg BD by mouth (PO) in conjunction with 240mg/24 hours furosemide IVI on diuresis and chloride homeostasis compared to 240mg/24 hours IV furosemide infusion alone (standard of care) both primary endpoints with the primary aim of gathering data on the feasibility and tolerability of the intervention which will inform a larger study.

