# Hull University Teaching Hospitals

1) Aged >18 of any gender and able to give informed consent (All women of child bearing potential (see appendix 3 for definition) must have a negative pregnancy test regardless of contraceptive use. The only form of contraception that will be allowed during the trial is abstinence.)

2) Heart failure of any aetiology (new or established diagnosis)

3) Admitted to hospital with a primary diagnosis of peripheral oedema caused by heart failure and deemed by treating clinicians to require treatment with intravenous diuretic.

4) Deemed to require standard of care – 10mg/hr continuous furosemide infusion.

5) Patients whose medications have been discontinued for other reasons  $\geq$ 48 hours previously may be considered eligible. These medications include; sodium glucose co-transporter 2 inhibitors, thiazide or thiazide-like diuretics, high dose aspirin ( $\geq$ 500mg / day), methotrexate, lithium, Sando-K®, sodium bicarbonate, other sodium tablets, oral steroids, or sodium valproate.

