# 7 TRIAL PROCEDURES

# 7.1 Recruitment

Patients will be identified as detailed below on cardiology wards at CHH and Hull Royal Infirmary (HRI) and screened for eligibility with consent by the study team. Data on patients age, gender, and eligibility status will be recorded anonymously to help define the generalisability of the results. We estimate the recruitment period will be for 30 weeks but can be extended to 52 weeks. We aim to recruit a minimum of 40 patients with a maximum of 50 during that time frame.

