# 7.4 Blinding

The trial will be an open label investigation without blinding for two reasons 1) we aim to collect pilot data to inform a larger blinded study 2) the primary endpoints and most secondary endpoints will not be susceptible to bias from unblinded treatment such as urine volumes and serum and urine electrolytes.

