The CRF will be considered as source documentation for the following items: Demography, symptom directed physical examination, vital signs, body weight and height, dates and times of visits and assessments. All other evaluations that are reported in the CRF must be supported by documentation in hospital notes or electronic medical record. CRFs are provided for each participant, and all data related to the trial will be recorded in these CRFs. The CRFs are to be completed at the time of the participant's visit so that they always reflect the latest observations on the participants. The investigator must verify that all data entries in the CRFs are accurate and correct by signing the relevant pages. If certain information is not available, not applicable, not done, or unknown, the research staff or investigator will enter the relevant abbreviation, i.e. N/A to confirm that the data field has not been overlooked. This also applies to participants who fail to complete the trial. If a participant withdraws from the trial, the reason must be noted on the CRF. If a participant is withdrawn from the trial because of an adverse event, a thorough effort should be made clearly to document the outcome. All forms should be completed using a black ballpoint pen and must be legible. All entries, corrections and alterations are to be made by the responsible investigator or her/his designee. Except for obvious mistakes, the corrections need to be commented. Corrections should be made in such a way that the original entry is not obscured. The corrected data should be entered, dated, and initialled by the investigator or his designee. On all trial-specific documents, other than the signed consent form and prescription, the participant will be referred to by the trial participant ID number, not by name.

Each contact with the participant will also be documented in the medical notes. As a minimum, the following information will be recorded in patient's medical records from trial visits or telephone contacts:

- Clearly written date of visit or contact, trial acronym and visit number.
- Date participant given participant information sheet
- Date consent form signed
- Date of screening
- Medical history, concomitant diseases and medication including trial medication, and any changes in concomitant diseases and medication at subsequent visits.
- Anything which is relevant to the ongoing care of the subject;
  - Relevant results and study medic's assessment of these results.

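### Section 8.9 ties the ban on starting SGLT2 inhibitors or thiazides to days on acetazolamide, so read literally it does not cover the standard-of-care arm

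*Protocol*

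**What the plan says.** Protocol Section 8.9 sets the only restriction on diuretic co-treatment after randomisation: "Starting sodium-glucose co-transporter 2 inhibitors or thiazide and thiazide-like diuretics will be contraindicated during the 4 days of treatment with ACZ". It makes one exception. A patient judged euvolaemic and ready to go home may be started on an SGLT2 inhibitor, and "this decision would be taken by the treating team and not the study team".

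Four other places bear on the point:

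- Section 8.8 treats both drug classes as diuretic, but as an entry rule: patients taking "drugs that have a notable diuretic effect thiazide and thiazide-like diuretics, and sodium-glucose co-transporter 2 inhibitors (SGLT2I) will be excluded". Exclusion criterion 4 in Section 6 does the same.
- Inclusion criterion 5 in Section 6 admits patients whose listed drugs were stopped at least 48 hours earlier: "These medications include; sodium glucose co-transporter 2 inhibitors, thiazide or thiazide-like diuretics", among others.
- Section 4 describes the treatment contrast as acetazolamide plus furosemide "compared to 240mg/24 hours IV furosemide infusion alone (standard of care").
- Section 7.4 states: "The trial will be an open label investigation without blinding".

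**The concern.** A restriction on co-treatment has to bind both arms equally if the difference between them is to be credited to the study drug. Here the restricted period is defined by exposure to the study drug, which controls never receive. The treating team knows the allocation and makes the prescribing decisions, and the drugs concerned act directly on a co-primary endpoint.

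Two things are at stake. The first is unequal diuretic co-treatment: a treating doctor who follows the text could start or resume an SGLT2 inhibitor in a control while holding back in an acetazolamide patient. The second is the per-protocol set. Section 10.1 limits it to patients who finish without a protocol deviation, and Section 10.6 presents it as the more accurate assessment of the primary endpoints. If the same drug start is a deviation in one arm and not in the other, membership of that set differs by arm because of wording alone.

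**Working it through.** The protocol states no figure on this point, so the check is mainly of the text.

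**Step 1: is there a ban for controls elsewhere?**

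- Section 6, exclusion 4, and Section 8.8 concern drugs being taken at entry. They do not govern a start after randomisation.
- Sections 3.1 and 4 describe the comparator as infusion alone. This implies that no second diuretic is added, but it defines a comparison and does not tell the treating team what not to prescribe.
- Section 9.2 makes adding a second diuretic for deterioration a serious adverse event, with no limit to one arm. That reports a start without barring it. An SGLT2 inhibitor begun for routine reasons is not such a deterioration.

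No explicit ban for controls is found.

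**Step 2: does the protocol name the arms when it needs to?** It is mixed.

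- In Section 7.8 the study-doctor visits give each arm its own clock: first dose for acetazolamide, randomisation for standard of care. Section 7.9 limits its mandatory withdrawal rule to the acetazolamide arm in so many words.
- Against that, the urine-collection instructions under Visits 2 and 4 are timed from the first acetazolamide dose and are not limited to that arm. Section 9.5 starts one reporting period at the first study-drug dose whatever the allocation.

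**Step 3: how could a control start arise?** The main route is an SGLT2 inhibitor started or resumed for routine reasons in a patient still on the infusion and not ready for discharge. Inclusion criterion 5 makes resumption possible. The protocol gives no rate.

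**Step 4: how large could it be?** This is an illustration only.

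Inputs from the protocol:

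- Section 7.1: "We aim to recruit a minimum of 40 patients with a maximum of 50 during that time frame". At 1:1 (Section 7.3.1) the minimum gives about 20 per arm.
- Section 10.1: lower target difference 500 mL/day; SD 500 to 1000 mL.

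Assumed inputs: 1 to 4 more starts among controls than among acetazolamide patients; 250 to 500 mL/day of added loss; effect present on 2 of the 4 days.

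Shift in control mean = excess share × added loss × (2/4).

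- Low end: 1/20 = 0.05; 0.05 × 250 × 0.5 = 6.25 mL/day; 6.25/500 = 1.25% of the target.
- High end: 4/20 = 0.20; 0.20 × 500 × 0.5 = 50 mL/day; 50/500 = 10% of the target.
- Equal starts with equal effect in both arms: shift 0.

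Standard error of the difference = SD × √(2/20) = 500 × 0.316 = 158 mL/day, up to 1000 × 0.316 = 316 mL/day. The shift is therefore between 6.25/316 = 0.02 and 50/158 = 0.32 standard errors. No figure is offered for chloride or for the per-protocol set.

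**The case against.** The strongest reply is that the sentence is shorthand. It stands under a heading about trial restrictions, next to rules on diet sheets and COVID-19 that apply to everyone. Step 2 shows that the protocol sometimes uses acetazolamide timing as a common clock. The comparator is infusion alone, and nothing suggests that the sponsor chose to let controls receive extra diuretics. Exposure is limited too: under Visits 4 and 5 in Section 7.8, a patient whose diuretic treatment is stepped down on day 3 or 4 is treated as having completed, with no further study investigations, so a start close to discharge has little room to act on the endpoints. All of this stands. It makes the intended meaning likely, but the instruction as written still omits one arm.

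A reader might also infer that later co-medication goes unrecorded, because the Schedule of Events marks concomitant medications at Visit 1 only. The documents do not support that. Section 11.1 requires the medical record of trial visits to note "any changes in concomitant diseases and medication at subsequent visits", Section 8.10 places all prescriptions in the electronic record, and the ward-round row, which includes treatment plans, is marked through Visit 6. The schedule is not part of this point.

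**Conclusion.** The wording defect is real and minor. Section 8.9 as written restricts SGLT2 inhibitors and thiazide-type diuretics only while a patient is on acetazolamide, and no other section supplies the missing rule for controls. It is best read as loose drafting.

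A reader might infer that the treatment comparison is biased towards no difference, or that power is materially reduced. For example, with 16 evaluable patients per arm, a true difference of 1000 mL/day and an SD of 1000 mL, power would fall from 80.7% to 72.1% if 10% of controls started a drug as effective as acetazolamide. The documents do not support such a claim. They give no start rate and no effect size for these drugs in this setting, and equal starts in the two arms would largely cancel. The range of 6 to 50 mL/day rests on the assumptions in step 4, and its upper end needs a fifth of controls to start a drug that adds as much daily loss as the trial's own lower target. The size and direction of any real bias are unknown.

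The effect on the per-protocol set is likewise a possibility under the literal reading and has not been shown to occur.

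**What to change.** Reword Section 8.9 so that starting or restarting an SGLT2 inhibitor, thiazide or thiazide-like diuretic is contraindicated in both arms from baseline to 96 hours, counted from the first acetazolamide dose in that arm and from randomisation in the standard-of-care arm. Keep the exception for an SGLT2 inhibitor in a euvolaemic patient who is ready for discharge, and apply it to both arms. State that a start outside the exception is a deviation whichever arm it occurs in, and that such patients stay in the randomised comparison.

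The cost is one sentence in a protocol amendment. It needs no extra procedure, data item or patient.

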# 8.10 Assessment of compliance

The study will rely on patient reported compliance however, pill taking during drug rounds in hospitals is done under nurse supervision and any concerns regarding non-adherence can be reported to the study doctors. All prescriptions and taking of medicines is recorded in the electronic health record.

# 8.11 Non-Investigational Medicinal Product (NIMP)

None

# 9 PHARMACOVIGILANCE

#### 9.1 Definitions

Term	Definition
Adverse Event (AE)	Any untoward medical occurrence in a participant to whom a medicinal product has been administered, including occurrences which are not necessarily caused by or related to that product.
Adverse Reaction (AR)	An untoward and unintended response in a participant to an investigational medicinal product which is related to any dose administered to that participant.
	The phrase "response to an investigational medicinal product" means that a causal relationship between a trial medication and an AE is at least a reasonable possibility, i.e. the relationship cannot be ruled out.
	All cases judged by either the reporting medically qualified professional or the Sponsor as having a reasonable suspected causal relationship to the trial medication qualify as adverse reactions.
Serious Adverse Event (SAE)	
 
A serious adverse event is any untoward medical occurrence that:
 
results in death
 
is life-threatening
 
requires inpatient hospitalisation or prolongation of existing hospitalisation
 
results in persistent or significant disability/incapacity
 
consists of a congenital anomaly or birth defect
 
Other 'important medical events' may also be considered serious if they jeopardise the participant or require an intervention to prevent one of the above consequences.
 
NOTE: The term "life-threatening" in the definition of "serious" refers to an event in which the participant was at risk of death at the time of the event; it does not refer to an event which hypothetically might have caused death if it were more severe.
 

Serious Adverse Reaction (SAR)	An adverse event that is both serious and, in the opinion of the reporting Investigator, believed with reasonable probability to be due to one of the trial treatments, based on the information provided.
Suspected Unexpected Serious Adverse Reaction (SUSAR)	
 
A serious adverse reaction, the nature and severity of which is not consistent with the information about the medicinal product in question set out:
 
in the case of a product with a marketing authorisation, in the summary of product characteristics MHRA approved (SmPC) for that product
 
in the case of any other investigational medicinal product, in the investigator's brochure (IB) relating to the trial in question
 

# 9.2 Operational definitions for (S)AEs

Due to the pilot and exploratory nature of this study **all** adverse events and adverse reactions will be recorded. All serious adverse events serious adverse reactions, and suspected unexpected serious adverse reactions will be reported.. This will enable collection on safety data for the use of ACZ concurrently with high dose loop diuretics as well as data on the tolerability of treatment for a future trial.

	Asymptomatic hypotension (systolic blood pressure (SBP) <90 mmHg)
	Symptomatic hypotension (SBP <90 mmHg and symptoms of: dizziness or presyncope)
	Asymptomatic hyponatraemia (serum sodium concentrations <130 mmol/L)
Adverse Events	Symptomatic hyponatraemia (serum sodium concentrations <130 mmol/L and symptoms of fatigue, nausea, vomiting, or headache not promoting further treatment or investigation)†
	Flare of gout requiring oral treatment and analgesia
	Decrease in estimated glomerular filtration rate >50% of baseline value
	† Treatment of headache with analgesia not included in this definition however treatment of nausea or vomiting with antiemetic is.
	Symptomatic hypotension with sequelae (SBP <90 mmHg and symptoms of: dizziness or presyncope and fall or injury as a direct result)
	Symptomatic hyponatraemia with sequelae (serum sodium concentrations <130 mmol/L and symptoms of fatigue, nausea, vomiting, headache which prompt further treatment or investigation,† or confusion or seizure deemed secondary to hyponatraemia).
	Decrease in eGFR >100% of baseline value or serum creatinine >221µmol/L
	Deterioration in condition during trial defined as:
Serious Adverse Events	
 
Deemed to need escalating doses of loop diuretic or the addition of a second diuretic agent such as thiazide diuretic.
 
Deemed to need inotropic support
 
New diagnosis of infection
 
New diagnosis of another concurrent illness that will prolong hospital stay
 
Transition to end-of-life care
 
Death
 

	Overdose of ACZ or furosemide infusion defined as 1) >500mg given per day of ACZ or 2) >240mg IV furosemide per day.
Adverse Reactions	Metabolic acidosis bicarbonate <23 mmol/L
	Hyperchloraemia 107-110 mmol/L

	Teaching Hospi	tals
	Any of the following possible side effects of acetazolamide that are NHS tolerable to the patient: haemorrhage, ataxia, depression, diarrhoea,	Trust
	dizziness, fatigue, flushing, irritability, headache, loss of appetite, nausea, vomiting, taste disturbance, paraesthesia.	
	Severe hyperchloraemia 107-110 mmol/L	
Serious Adverse	Severe metabolic acidosis bicarbonate <20 mmol/L	
Reactions	Any of the possible side effects of acetazolamide listed in the MHRA	
	approved SPC that are intolerable to the patient and lead to	
	investigations.	
Suspected Unexpected Serious Adverse Reactions	Any SAR that is not expected based on the MHRA SPC for acetazolamide in relation to the nature and severity of the SAR will be reported as SUSAR. Due to the lack of data on the safety and tolerability of acetazolamide in modern patients with heart failure treated with high dose loop diuretic we will consider any SAR that occurs in >5% of patients as a SUSAR	

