# 3.5 Secondary endpoints/outcomes

All secondary endpoints are exploratory designed to inform future research.

Differences between the two groups during the 4 day treatment period in:

1) daily weight

2) serum electrolyte levels (sodium, bicarbonate and potassium)

3) incidence of electrolyte abnormalities; hyponatraemia (<135 mmol/L), hypochloraemia (<96 mmol/L), hypokalaemia (<3.5 mmol/L), high (>30 mmol/L) or low (<22 mmol/L) serum bicarbonate.

4) change in renal function measured by serum creatinine (µmol/L) and estimated glomerular filtration rate (eGFR) (ml/min/1.72m2)

5) change in urinary electrolyte levels after 48 and 96 hours of treatment; sodium, chloride, potassium.

- 6) clinical assessment of congestion
- 7) ultrasound measures of congestion period; inferior vena cava (IVC) diameter
- 8) change in breathlessness score using the Likert scale.
- 9) time to clinical euvolaemia and end of intravenous therapy

10) length of stay

11) rate of adverse reactions, serious adverse reactions and suspected unexpected serious adverse reactions – treatment arm

- 12) rate of adverse events and serious adverse events both arms
- 13) rate of recruitment to study
- 14) time taken to screen & recruit
- 15) rate of drop-out after randomisation cause specific
- 16) Cause specific hospitalisation or mortality after 30 days and 180 days follow up.

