#### Exclusion criteria

1) Unable to give informed written consent

2) Allergy or contraindication to carbonic anhydrase inhibitors

3) Patient thought to be at end-of-life

4) Concurrently taking thiazide (or thiazide-like) diuretic or sodium-glucose linked transporter-2 inhibitor, high dose aspirin (>500mg / day), methotrexate, lithium, or sodium valproate, oral steroids Sando-K®, oral sodium bicarbonate, or other sodium tablets

5) Severe anaemia (haemoglobin <8 g/DL); or severe infection (investigator opinion).

6) SBP <80 mmHg at randomisation

7) Serum sodium (severe hyponatraemia) <130 mmol/L at randomisation

8) Serum potassium (hypokalaemia) <3.5 mmol/L at randomisation

9) Serum chloride (severe hyperchloraemia) >110 mmol/L at randomisation

10) Severe renal dysfunction with an eGFR (estimate glomerular filtration rate) result of  $\leq$ 20 ml/min calculated by the Cockcroft-Gault formula

12) Pregnant or breast feeding, or intends to become pregnant whilst taking part in the trial

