# 9.5 Reporting Period

Study doctors will assess for adverse events or reactions at each visit and can be alerted by email or telephone by the ward staff, the patient will be assessed as soon as is practical and within 12 hours of the alert. The reporting period for AE and SAEs starts from the date and time of consent, and the reporting period for AR, SAR, and SUSARs starts from the first IMP dose regardless of treatment allocation (ACZ or SoC). The monitoring period for events will be from 5 days from baseline but data on all adverse events will be collected up to the point of discharge from the written and electronic medical record.

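### Several section 9.2 event thresholds are absolute values that eligible patients can already meet at entry, with no requirement that the value be new or worse

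*Protocol*

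**What the plan says.** Section 9.2 lists, among others:

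- adverse event: "Asymptomatic hypotension (systolic blood pressure (SBP) <90 mmHg";
- adverse reactions: "Metabolic acidosis bicarbonate <23 mmol/L" and "Hyperchloraemia 107-110 mmol/L";
- serious adverse reactions: bicarbonate below 20 mmol/L and "Severe hyperchloraemia 107-110 mmol/L";
- serious adverse event: a fall in eGFR of more than 100% from baseline or, as an alternative that suffices alone, creatinine above 221 µmol/L.

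The section 6 exclusions include "SBP <80 mmHg at randomisation" and "Serum chloride (severe hyperchloraemia) >110 mmol/L at randomisation". Renal exclusion is by Cockcroft-Gault, at 20 ml/min or below in section 6 and at 30 ml/min or below in the Trial Summary. Neither place sets a bicarbonate or creatinine limit.

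On timing, section 9.5 states: "The reporting period for AE and SAEs starts from the date and time of consent". The same sentence starts AR, SAR and SUSAR reporting at the first IMP dose, for either allocation. Section 3.5 includes as an endpoint the "rate of adverse reactions, serious adverse reactions and suspected unexpected serious adverse reactions – treatment arm", and separately the AE and SAE rates in both arms. Section 9.4 requires SAEs and SARs to reach the sponsor within 24 hours. It also treats any SAR in more than 5% of patients, or any AR in more than 10%, as a SUSAR.

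**The concern.** A fixed cut-off measures harm on trial only if patients start on the safe side of it, or if the definition asks for a change. Here some eligible patients start on the wrong side and no change is asked for. Followed as written, section 9.2 turns a stable pre-existing value into an event.

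Section 4 gives feasibility and tolerability data as the primary aim, and section 9.2 says its event data are meant to inform a future trial. Inflated rates would carry into that trial's planning. They would also create expedited reports about patients whose condition has not changed, and add to the counts behind the SUSAR escalation rule.

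**Working it through.** The protocol states no figure to reproduce here. The check sets each threshold beside its entry limit.

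| Item in 9.2 | Class | Entry limit | Eligible values that already meet it |
|---|---|---|---|
| SBP <90 mmHg | AE | <80 excluded | 80-89 mmHg |
| Chloride 107-110 mmol/L | AR and SAR | >110 excluded | 107-110 mmol/L |
| Bicarbonate <23 / <20 mmol/L | AR / SAR | none | any value below 23 / 20 |
| Creatinine >221 µmol/L | SAE | none on creatinine; Cockcroft-Gault ≤20 or ≤30 ml/min | depends on age, sex, weight |
| Sodium <130 mmol/L | AE | <130 excluded | none |
| eGFR fall | AE / SAE | relative to baseline | none |

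**Creatinine.** Cockcroft-Gault = k × (140 − age) × weight / creatinine in µmol/L, with k = 1.23 for men and 1.04 for women. The constants, ages and weights are assumptions, not protocol figures. For a man aged 75 weighing 75 kg with creatinine 221: 1.23 × 65 × 75 / 221 = 27.1 ml/min. His numerator is 5996.25, so the creatinine at which he reaches each limit is 5996.25 / 20 = 299.8 and 5996.25 / 30 = 199.9 µmol/L. Other examples:

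| Patient | ml/min at creatinine 221 | Creatinine at the 20 limit | Creatinine at the 30 limit |
|---|---|---|---|
| Man, 75 y, 75 kg | 27.1 | 299.8 | 199.9 (no overlap) |
| Man, 75 y, 90 kg | 32.6 | 359.8 | 239.9 |
| Woman, 75 y, 75 kg | 22.9 | 253.5 | 169.0 (no overlap) |
| Man, 70 y, 100 kg | 39.0 | 430.5 | 287.0 |

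At age 75 the overlap under the 30 ml/min limit needs a weight above 30 × 221 / (65 × 1.23) = 82.9 kg for a man and 30 × 221 / (65 × 1.04) = 98.1 kg for a woman. Under the 20 ml/min limit the corresponding weights are 55.3 and 65.4 kg.

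**SUSAR triggers.** The smallest count above a share s of n patients is floor(s × n) + 1. The protocol does not say whether its percentage is of the acetazolamide arm or of all patients.

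| n | SARs to exceed 5% | ARs to exceed 10% |
|---|---|---|
| 20 to 27 (acetazolamide arm) | 2 | 3 |
| 40 (all) | 3 | 5 |
| 50 (all) | 3 | 6 |

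Suppose a share p of 20 acetazolamide patients enters with bicarbonate below 23 and stays there after dosing. The binomial chance that these alone reach 3 is 0.075 at p = 5%, 0.32 at 10% and 0.79 at 20%. These values of p are assumptions.

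**Chloride.** Appendix 2 gives an admission median of 100 and SD of 3 mmol/L in patients with normal admission chloride. On a normal approximation, P(107 to 110) = 0.009, or 0.015 allowing for rounding to whole units. That is 40 × 0.009 = 0.4 to 40 × 0.015 = 0.6 patients in 40. The subgroup is selected and measured at admission, so this is indicative only.

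**The case against.** The strongest reply has five parts.

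*Timing.* A reader might infer that the baseline bicarbonate or chloride reading itself registers as a reaction. Section 9.5 does not support that: AR and SAR reporting starts at the first dose, so such a value counts only if it persists or recurs afterwards. For SBP and creatinine the window does open at consent. The schedule in 7.7 marks event assessment only from Visit 3, but an unchanged value would still meet the definition then.

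*Control comparison.* A reader might also infer, from the treatment-arm-only endpoint, that no control rate exists. For bicarbonate that is wrong: 10.3.3 compares the proportion below 23 mmol/L between arms. SBP and creatinine events are reported in both arms. Change in chloride is a co-primary endpoint, but the 107-110 item itself has no stated comparison.

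*Causality.* Section 9.1 defines a reaction as a related response, 9.4 requires causality review of serious events, and 9.3 refers to clinically significant laboratory abnormalities. This leaves room for judgement. It sets no baseline rule, and 9.2 lists the values outright as reactions.

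*Size.* The creatinine overlap is not general under both renal limits. The chloride share is probably small. Patients enter on furosemide, for which 8.7 lists metabolic alkalosis as common, so low bicarbonate at entry may be infrequent. All of this stands.

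*Intent.* Section 9.2 deliberately records all events, and treatment-emergent tables could be left to an analysis plan. A later table would not, however, undo 24-hour reports or SUSAR escalations already triggered by the protocol definitions.

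**Conclusion.** The point holds for four items: SBP, chloride, bicarbonate and absolute creatinine. It does not hold for sodium or the eGFR-fall criteria, so a claim that the 9.2 thresholds overlap entry in general would be too broad.

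SBP and creatinine can be met from consent, and affect both arms equally in expectation. Bicarbonate and chloride count when a pre-existing value persists after dosing. The creatinine overlap is wide under the 20 ml/min limit and confined to heavier or younger patients under the 30 ml/min limit.

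The consequence is mainly inflated absolute AE, SAE, AR and SAR rates, SAE reports without clinical change, and inflated counts towards the SUSAR triggers. With 20 to 27 acetazolamide patients, 2 SARs or 3 ARs are enough. The documents do not give the number of patients entering past a threshold; the probabilities above rest on assumed shares and on persistence after dosing. Because the rule is cheap to add and tolerability is a stated aim, the change should be made.

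**What to change.** In 9.2 and on the adverse event form, count the SBP, chloride, bicarbonate and absolute creatinine items as AE, AR, SAE or SAR only when treatment-emergent: not met at the day 1 pre-dose reading, or met and worsened from it by an amount that the sponsor states. Name the equivalent day 1 reading for the control arm, which has no first dose. Tabulate the chloride 107-110 item in both arms beside the bicarbonate comparison already planned.

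Three sets of passages also need reconciling by the sponsor: 9.2 with section 6; the 20 and 30 ml/min renal limits; and chloride 107-110, which 9.2 labels both AR and SAR while 7.9 calls it mild. This review takes no view on which limit or label is right.

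The cost is wording. SBP, electrolytes and creatinine are already collected at baseline under 7.6 and 7.7. The change alters counting only, not entry, dosing, monitoring or withdrawal. The downside is that fewer events are counted; a listing of values already past a threshold at baseline would keep them visible.
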